## 7.11 End-of-Treatment Visit

Within 1 week following the final dose of TTI-621 (or at the time of premature discontinuation of treatment), the following procedures will be performed:

- physical examination and ECOG score
- body weight
- vital signs
- disease assessment (if not performed within the last 8 weeks)
- QOL by FACT-G (all subjects) and SKINDEX29 (CTCL only)
- resting 12-lead ECG
- serum for PK
- serum chemistries
- hematology

- coagulation panel
- TSH (only for subjects in the nivolumab combination cohort)
- urinalysis
- serum for ADA analysis
- biomarkers (see Study Manual for details of sample preparation and shipping):
  - serum for cytokine/chemokine panel (not required for Part 4)
  - whole blood for innate and adaptive response assay (not required for Part 4)
- AEs
- concomitant medications
- peripheral blood and blood smear for central pathology for SS patients (Part 3 only). Refer to the Laboratory Manual and to [Appendix D. Table 3](#) for additional information.

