#### 8.4.6 Efficacy Analyses

Efficacy analyses will be conducted using the Full Analysis Set and, where appropriate, the Per-protocol Set; in addition, the overall response rate will also be presented for the Response-Evaluable Set.

The overall response rate will be estimated for each cohort using disease-specific response criteria (see [Section 7.14.1](#)). The duration of response (DOR) will be calculated for a subject who achieves a response, and is defined as the number of weeks from the start date of the response (and subsequently confirmed) to the first date recurrent or progressive disease is documented. If a subject dies, irrespective of cause, without documentation of recurrent or progressive disease beforehand, then the date of death will be used to denote the response end date.

Progression-free survival (PFS) is defined as the number of weeks from the date of the first dose of study drug to the earliest of documented recurrent or progressive disease or death due to any cause without prior progression. Leukemia-free survival (LFS) will be calculated in the same manner, as appropriate.

DOR and PFS will be summarized descriptively using the Kaplan-Meier method with 95% CI calculated using Greenwood's formula. Median follow-up for each endpoint will be estimated according to the Kaplan-Meier estimate of potential follow-up. The PFS rate at selected landmarks (e.g., 6 months) and corresponding 95% CIs will be estimated using the Kaplan-Meier method. Greenwood's formula will be used to calculate the standard errors of the Kaplan-Meier estimate and upper and lower limits of the 95% CI.

For DOR and PFS, subjects who meet one or more of the following conditions will be right-censored as follows:

- subjects with no baseline or postbaseline disease assessments unless death occurred prior to the first planned assessment (in which case the death will be considered a PFS event)
- subjects who initiate subsequent anticancer therapy in the absence of documented progression
- subjects who die or have disease progression after missing 2 or more consecutively scheduled disease assessment visits
- subjects who are last known to be alive and progression-free on or before the data cut-off date

For such subjects, the progression or censoring date will be determined based on described conventions (Food and Drug Administration, 2007), as outlined in the SAP.

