### **3.7.2 Duration of Response and Progression Free Survival Time**

The time-to-event endpoints measured in this study are defined in terms of the following dates.

- Date of first dose = Date of first dose as recorded on Treatment CRF
- Date of response = Earliest of the consecutive dates at which subject is assessed in a responder category
- Date of last non-PD assessment = Date of last non-missing assessment other than NE, NA, or Unknown
- Date of progression = Date at which subject is first assessed as having progressive disease
- Date of initiation of anticancer treatment = Earliest concomitant medication start date for concomitant medications identified by sponsor as being anticancer treatments

- Date of death = Date of death from any cause as recorded on Death Page CRF

The following time-to-event endpoints will be calculated for each subject.

- DOR for subjects who achieved an objective response = Duration of response (in weeks) =  $[\min(\text{Date of progression}) - \text{Date of response} + 1]/7$
- PFS = Progression free survival time (in weeks) =  $[\min(\text{Date of progression}, \text{Date of death}) - \text{Date of first dose} + 1]/7$

In the case of missing dates (ie, subjects without an event), the following censoring rules will be applied.

Endpoint	Censor if:	Censoring date = Minimum of indicated dates		
		Date of last non-PD assessment	Date of initiation of anticancer treatment	Date of death
DOR	Death prior to progression			X
DOR or PFS	Subsequent anticancer therapy is initiated in the absence of documented progression		X	
	Death or progression after $\geq 2$ assessments of NE, NA, Unknown, or Missing	X		
	Alive & progression free	X	X	

DOR and PFS will be displayed in listings.

The number of subjects with event for DOR and PFS will be summarized. Median time to event, the 25th and 75th percentiles of time to event, along with 95% CI for DOR and PFS will be estimated according to the Kaplan-Meier estimate using the Brookmeyer-Crowley method.

Additionally, the PFS rate at selected landmarks (e.g., 6 months) and corresponding 95% CIs will be estimated using the Kaplan-Meier method. Greenwood's formula will be used to calculate the standard errors of the Kaplan-Meier estimate and upper and lower limits of the 95% CI.

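### Two rows of the SAP 3.7.2 censoring table give different dates for a living, progression-free subject who starts new anticancer therapy, and no precedence is stated

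*SAP*

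**What the plan says.** The table in SAP 3.7.2 is introduced with "In the case of missing dates (ie, subjects without an event), the following censoring rules will be applied". Its date columns are headed "Censoring date = Minimum of indicated dates", so within a row the earliest marked date applies. Four rows matter here:

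| Row | Endpoint | Dates marked | Resulting censoring date |
|---|---|---|---|
| "Subsequent anticancer therapy is initiated in the absence of documented progression" | DOR, PFS | therapy start | therapy start |
| "Alive & progression free" | DOR, PFS | last non-PD assessment; therapy start | the earlier of the two |
| Progression or death after two or more unevaluable or missing assessments | DOR, PFS | last non-PD assessment | last non-PD assessment |
| "Death prior to progression" | DOR only | death | death |

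The assessment date is defined by "Date of last non-PD assessment = Date of last non-missing assessment other than NE, NA, or Unknown". The therapy date comes from concomitant medications that the sponsor identifies as anticancer treatment.

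Protocol 8.4.6 lists "subjects who initiate subsequent anticancer therapy in the absence of documented progression" among those to be right-censored, but gives no date and refers to the SAP for it.

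**The concern.** The new-therapy and alive rows overlap. The therapy column in the alive row has an effect only for a subject who has started new therapy, so living switchers without progression evidently belong there. They also meet the new-therapy row exactly. Two programmers could each follow the SAP and produce different PFS and DOR for the same subject.

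The choice affects the estimate as well as its reproducibility. Under the new-therapy row a subject stays in the Kaplan-Meier risk set from the last assessment until therapy begins, with no scheduled assessment in that interval. With the events held fixed, later censoring can only enlarge the risk sets, so the curve under that row is never below the curve under last-assessment censoring. The missed-assessment row of the same table deals with a similar gap by going back to the last non-PD assessment.

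**Working it through.** **No plan figure to reproduce.** Neither document states an expected PFS or DOR.

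**How long the gap can be**
- Protocol Appendix D Table 3 schedules T-cell lymphoma assessments at the end of Weeks 8, 16 and 24, then every 12 weeks.
- The end-of-treatment visit (Protocol 7.11) lists "disease assessment (if not performed within the last 8 weeks" in its requirements. The last assessment can therefore be up to 8 weeks old at that visit.
- Concomitant medications are recorded through the safety follow-up visit (Protocol 7), about 30 days after the last dose (Protocol 7.12): 30/7 = 4.3, about 4 weeks.
- Longest credited gap: 8 + 4 = about 12 weeks.

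**One subject, two dates.** The SAP formula is PFS = (date − first dose + 1)/7. Take stable disease at the end of Week 8 (Day 56), treatment stopped at Week 15, and new therapy at the end of Week 18 (Day 126), with the subject alive and without documented progression. At Week 15 the last assessment is 15 − 8 = 7 weeks old, so no end-of-treatment assessment is required.
- New-therapy row: 126/7 = 18 weeks.
- Alive row: min(56, 126)/7 = 8 weeks.

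A similar record can cross the 6-month landmark. With the last assessment on Day 168 and therapy on Day 245, the two dates are 245/7 = 35 weeks and 168/7 = 24 weeks. The subject is still at risk at Week 26 under one row and already censored under the other.

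**Effect on 6-month PFS.** These inputs are assumptions, not in the documents:
- exponential PFS with median 12 or 20 weeks, so true 26-week PFS is 0.5^(26/12) = 22.3% or 0.5^(26/20) = 40.6%;
- time to leaving without progression with median 24 or 60 weeks, which makes about 19-37% of subjects switch in the first case and 27-49% in the second;
- therapy starting uniformly within 4 weeks of leaving;
- half of progressions found between scans.

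The scan schedule and the 8-week end-of-treatment rule follow the protocol. With 200,000 simulated subjects per scenario, the mean credited gap is 5.5-5.6 weeks and the maximum 12. Kaplan-Meier at 26 weeks:

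| True value | Censored at therapy start | Censored at last assessment |
|---|---|---|
| 22.3% | 24.4-25.8% | 21.7-22.8% |
| 40.6% | 42.9-44.5% | 40.1-41.1% |

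The smallest difference is 24.4 − 22.8 = 1.6 points. The largest is 44.5 − 40.1 = 4.4 points, or 44.2 − 39.7 = 4.5 in a repeat run.

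**Sensitivity**
- If no progression is found between scans, the difference falls to about 1.0-2.7 points. The last-assessment rule is then itself 2.6-3.1 points above the true value, because of scan spacing.
- If all progressions are found between scans, the last-assessment rule falls below the true value, and therapy-start censoring is sometimes the closer of the two.
- A separate simulation used n = 35, median PFS 12-30 weeks, 10-40% switching, the ±1 week assessment window and therapy before the next scan. The difference was 0.4-4.1 points. With every scan exactly on schedule and no event between scans, it was zero.

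**The case against.** The strongest reply is that the SAP already contains the right answer. The alive row takes the earlier date, and if the minimum in the column header were applied across every row a subject meets, the last assessment would usually win. That is a sensible reading, but the SAP does not state it: the marks are set row by row, and on that reading the separate new-therapy row would have no effect for living subjects. What stands is that a reader might infer that the SAP has settled on therapy start for everyone who switches. The table does not support that. It supports an unresolved overlap, and every figure above is conditional on the new-therapy row being the one applied.

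A reader might also infer that nobody looks for progression after the last scan. That goes too far. On treatment, an assessment is triggered by observed or suspected clinical progression (Protocol 7.10). The end-of-treatment visit includes a physical examination, and long-term follow-up asks for a progression date not documented earlier (Protocol 7.13). What is missing is a scheduled disease assessment.

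Gaps and biases much larger than those shown are tempting too, if therapy is assumed to start months after treatment ends. The SAP takes the therapy date from concomitant medications, and collection of these stops at the safety follow-up visit, so a lag much beyond 4 weeks lies outside that source.

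Finally, the effect is small next to sampling error. At n = 35, ignoring censoring, the approximate 95% half-width is 1.96 × √(0.223 × 0.777/35) = 14 points, or 1.96 × √(0.406 × 0.594/35) = 16 points. This is true and limits the importance of the point. It does not remove the ambiguity, which depends on no assumption.

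**Conclusion.** The overlap is established from the text alone: a living switcher without documented progression has two possible censoring dates, with no precedence stated in the SAP or the protocol. For DOR the death row adds a third kind of date. A responder who starts new therapy and then dies without progression meets both that row and the new-therapy row.

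If the new-therapy row is used, up to about 12 weeks per switching subject are credited as progression-free without a scheduled assessment, and 6-month PFS is about 1.6-4.5 points higher than with last-assessment censoring under the assumptions listed. The documents give no switching rate, lag or true PFS, the last-assessment rule is not itself unbiased, and the DOR effect was not quantified.

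A reader might infer that the Part 3 go/no-go rule is affected. It is not. PFS and DOR are secondary and descriptive, and the Simon boundaries count responders only. The synopsis allows durability of response to inform the Stage 2 decision, but attaches no threshold to it. The point is worth correcting for reproducibility and internal consistency; it does not threaten the design.

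**What to change.** In SAP 3.7.2:

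1. In the new-therapy row, set the censoring date to the last evaluable non-PD assessment on or before the start of new anticancer therapy. For PFS, use Day 1 if there is none.
2. In the alive row, use the same date when new therapy was started, so that the rows agree.
3. State that the new-therapy rule takes precedence over the other rows, including the DOR death row, when therapy began before progression or death. Aligning the two rows without this sentence would leave the DOR death row in conflict.

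The cost is one table cell and one sentence. No new data, visits or changes in conduct are needed. Reported PFS and DOR may be slightly shorter.

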### **3.7.3 Organ system-specific overall response rate**

In subjects with CTCL and PTCL (in Parts 3 and 4), the organ system-specific response rates will be presented by: in skin, lymph nodes, blood, and visceral organs. (Olsen, 2011)

## 5 Tables, figures, and listings

A separate document will be maintained that identifies all tables, figures, and listings (TLFs) to be provided for the CSR. This document will be updated as appropriate during TFL development.
